Tanzania National Institute for Medical Research and Muhumbili Medical Center

London School of Hygiene and Tropical Medicine

University of Malawi, Blantyre College of Medicine

Malawi Ministry of Health

Introduction

This document (Statistical Analysis Plan, SAP) describes the planned analysis and reporting for the clinical trial, **Mortality Reduction after Oral Azithromycin**, Contingency Study, Years 3-4, Niger. It includes specifications for the statistical analyses and tables to be prepared for the interim and final Clinical Study Report. This study is a Phase IV clinical trial to compare methods to reduce childhood mortality using mass administration of azithromycin (Pfizer, CAS 83905-01-5) compared to placebo. The content of this Statistical Analysis Plan meets the requirements stated by the US Food and Drug Administration and conforms to the American Statistical Association's Ethical Guidelines.

The following documents were reviewed in preparation of this Statistical Analysis Plan:

- Mortality Reduction after Oral Azithromycin, Protocol
- Mortality Reduction after Oral Azithromycin, Statistical Analysis Plan
- Mortality Reduction after Oral Azithromycin, Manual of Operations
- ICH Guidance on Statistical Principles for Clinical Trials

The planned analyses described in this SAP will be included in future manuscripts. Exploratory analyses not necessarily identified in this Statistical Analysis Plan may be performed to support the analysis. Unplanned analyses not delineated in this Statistical Analysis Plan will be documented as such in the final Clinical Study Report and manuscripts.

This document will be reviewed prior to the enrollment of patients. All subsequent changes will be indicated by detailed change log in the Appendix.

MORDOR Stage 2 Contingency Study

1 Introduction

Should the primary analysis of azithromycin to prevent mortality reveal evidence of a benefit, we propose to proceed with two additional studies in Stage 2.

2 Design

Contingency study A. All communities in Niger will receive treatment at the conclusion of MORDOR Stage 1 (original study). Specifically, azithromycin communities will continue with azithromycin, and placebo communities will receive azithromycin at the 24 month visit (census number 5). Follow-up will occur at month 30 and month 36, providing one additional year of data.

Contingency study B. At the 36 month visit, rerandomization will occur, and half of communities will begin to receive placebo.

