 - a. Analysis of the seasonality and timing of deaths: time of death, time of treatment for those who died, and time since treatment for all deaths. We will conduct comparisons of time since treatment conditional on death based on the Cramer-von Mises test (exactly as in Stage 1), additionally comparing across treatment arms and longitudinally. Comparisons of equality of circular means will be used to assess seasonality of death and of treatment, comparing between randomization arms and longitudinally. We will, in particular, focus special attention and reporting to a comparison of phases 1-4 to 5-6 within the placebo arm.
 - b. Analysis will be reported according to the same age classes used in the original study (Keenan et al, NEJM, 2018), i.e. 1-5, 6-11, 12-23, 24-59 months.
 - c. We will examine the difference between phase 5 and 6 in the same way.
 - d. We will report longitudinal analysis of mortality changes in the original azithromycin arm, using a linear predictor of study interval (1-6).
 - e. We will compare estimated treatment effect at a regional level using placebo mortality rates as a predictor.

Study B (year two of mortality contingency study)

- 1. Sample size considerations are the same as in Study A (year 1).
 - a. Assuming communities of size 668 with approximately 17% in the target age range, an effect size of 20%, 10% loss to follow-up per year, 2% mortality per year, and a CV of 0.51, 312 communities per arm provides approximately 87% power (see MORDOR Phase I SAP for details).
 - b. Updating based on data from Phase I (Niger), we find the following. Assuming the observed CV of 0.34, a death rate of 2% per year results in approximately 80% power to detect a 17% effect. A death rate of 2.5% per year (and a CV of 0.34) result in approximately 80% power to detect a 15.5% effect size.
- 2. The primary prespecified analysis will contrast the rerandomized placebo arm with the rerandomized azithromycin arm. This will be conducted with negative binomial regression, using a two-sided alpha of 0.05 and a permutation test by randomization arm.
- 3. Supplementary analyses will control for prior history (original randomization arm).
- 4. Longitudinal analysis for communities who always received azithromycin will be reported.
- 5. We will compare all four groups for the last year of data (two histories by two final treatments).
- 6. Additional analyses by the same age groups as before and by phase will be reported.

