- 7. Models of timing, seasonality, and geography will be reported as secondary analysis.

Morbidity Study. Analysis of morbidity communities will follow the exact template as Stage I. Primary prespecified analyses will be two-sided, at an alpha of 0.05. However, the morbidity communities are still receiving placebo. Note that we will report the full follow-up at 48 months separately from the Stage 1 primary analyses. We will also look for secular effects longitudinally over the four years of the full study, as well as phases 5-8 separately.

- 1. Anthropometry: we will examine height and weight longitudinally, and WFH Z score secondarily. Please see the Stage 1 SAP for details.
- 2. Other analyses will include drug resistance and malaria, as in Stage 1.
- 3. Note that we do not do nares or conjunctiva swabs, conjunctival photos, or any swabs on 7-12 year olds in the contingency study.

Statistical considerations

- 1. Communities which drop out of the study will be omitted from analysis for all study period for which we have no data for that community. If a community rejoins at a particular phase, it will be included as before.
- 2. Evidence of poor model fit to the negative binomial regression will justify reporting additional models.
- 3. Permutation tests will be conducted with 10000 replications. If the critical value 0.05 lies within the Monte Carlo confidence interval for the P-value, we will replicate with 10,000,000 replications, and this will be reported.

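### Study B's primary model leaves out each community's mortality before the month-36 rerandomization, a valid baseline covariate worth 0 to about 4 points of power at the observed CV

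*SAP*

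**What the plan says.** Contingency Study SAP, section 2 (Design), Study B: "At the 36 month visit, rerandomization will occur, and half of communities will begin to receive placebo". Section 3, Study B, item 2 sets the primary contrast: "The primary prespecified analysis will contrast the rerandomized placebo arm with the rerandomized azithromycin arm". It adds: "This will be conducted with negative binomial regression, using a two-sided alpha of 0.05 and a permutation test by randomization arm". No covariate is named. The Stage 1 primary model (SAP 2.1.1) has country as its only regressor beyond treatment, and country has no role in a Niger-only study.

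History enters Study B only through the original arm. Item 3 controls for it in supplementary analyses, and item 5 crosses it with the final treatment. Item 4 is longitudinal within communities that always received azithromycin, so it is not a between-arm contrast. Item 7 adds timing, seasonality and geography. None of these uses a community's own earlier mortality.

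On power, Study B item 1a assumes "an effect size of 20%, 10% loss to follow-up per year, 2% mortality per year, and a CV of 0.51" and concludes that "312 communities per arm provides approximately 87% power". Item 1b updates this with the observed CV of 0.34: about 80% power for a 17% effect at 2% mortality, or for a 15.5% effect at 2.5%.

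**The concern.** Stage 1 records deaths and person-time by community over four six-month intervals (Protocol 4.2; SAP 2.1.1), and Study A adds months 24-36. All of this precedes the Study B assignment. Adjusting for it cannot bias the Study B contrast, and it may remove some between-community variance.

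The same SAP already adjusts for baseline elsewhere. The clinic case-count model uses the preceding year's count (2.1.3.6), and the secondary morbidity models use baseline values (2.1.2).

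Study B has one year of follow-up and is the plan's only randomized comparison of stopping with continuing azithromycin. By its own update it has about 80% power for effects of 15.5-17%, so precision that costs no data collection is worth considering.

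**Working it through.** **Inputs.** Study B item 1 gives community size 668, 17% in the age range, 10% loss per year and 312 communities per arm. It also gives the CV (k), mortality rate and effect of each scenario. Follow-up is taken as one year, months 36-48. Person-years per community: y = 668 × 0.17 × 0.90 = 102.2.

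**Step 1: reproduce the stated power.** The formula in SAP 3.1, solved for power, is

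power = Φ( √[(c − 1)(λ0 − λ1)² / V] − 1.96 ), with V = (λ0 + λ1)/y + k²(λ0² + λ1²).

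For λ0 = 0.02, λ1 = 0.0166, k = 0.34:
- V = 0.0003581 + 0.0000781 = 0.0004362.
- √(311 × 0.0034² / 0.0004362) = 2.871.
- Power = Φ(0.911) = 81.9%, against about 80% stated.

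The 15.5% effect at 2.5% mortality gives 81.3% (stated about 80%). The 20% effect at 2% mortality with CV 0.51 gives 87.0% (stated 87%).

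**Step 2: add the covariate.** Only the second term of V can shrink. Replace k² by k²(1 − rho²R). Here rho is the correlation of true community rates between months 0-36 and months 36-48. R = k²/(k² + 1/μ) is the reliability of the earlier observed rate, where μ is expected prior deaths per community. For former placebo communities μ = y(2λ0 + λ1), because they had two years of placebo and one of azithromycin. For former azithromycin communities μ = 3yλ1. R is averaged over the two groups.

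| Scenario | μ (placebo / azithromycin) | R | Power at rho 0 | rho 0.5 | rho 1 | Variance reduction at rho 0.5 / 1 |
|---|---|---|---|---|---|---|
| CV 0.34, 2%, 17% effect | 5.8 / 5.1 | 0.386 | 81.9% | 82.5% | 84.5% | 1.7% / 6.9% |
| CV 0.34, 2.5%, 15.5% effect | 7.3 / 6.5 | 0.442 | 81.3% | 82.2% | 85.0% | 2.4% / 9.5% |
| CV 0.51, 2%, 20% effect | 5.7 / 4.9 | 0.579 | 87.0% | 88.5% | 92.9% | 4.7% / 18.9% |

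In the two CV 0.34 rows, between-community variation is only 18% and 22% of V (0.0000781/0.0004362 in the first). This caps the gain. At rho 0.3 it is 0.2-0.3 points.

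**Step 3: express it as communities.** The equivalent extra communities per arm are 311 × (V/V_adjusted − 1). At CV 0.34 this is about 5-8 at rho 0.5 and 23-33 at rho 1.

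**Step 4: checks.** If μ is instead computed at the control rate for all three years, the maximum gains at CV 0.34 are 2.8 and 3.9 points, rather than 2.6 and 3.7. With months 24-36 alone, the maxima are 1.3 and 1.9 points. A simulation of 624 communities (CV 0.34, 600 trials per cell), fitting the negative binomial model with the covariate described under the fix, gave these falls in mean squared standard error:
- 17% effect at 2% mortality: 0.0, 1.6 and 6.7% at rho 0, 0.5 and 1.
- 15.5% effect at 2.5% mortality: 0.0, 2.3 and 9.4%.

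These agree with the formula.

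**The case against.** The strongest reply is that nothing here is wrong. The unadjusted permutation test is valid, the power claim reproduces, and an unadjusted primary with adjusted supplementary analyses is a legitimate choice. It also keeps one model family across Stage 1, Study A and Study B. All of that stands, and it is why the point is optional.

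The gain is also small and uncertain. It rests on a correlation the documents do not report, it is under 1 point at rho 0.5 with CV 0.34, and its upper end needs perfectly persistent community rates. That stands too. At item 1a's 20% effect combined with the observed CV of 0.34, unadjusted power is already 92.6% (2% mortality) or 96.2% (2.5%). The most that adjustment adds there is about 1.5 points. The 17% and 15.5% effects used above are nevertheless the SAP's own pairings with CV 0.34, and the calculated gain is not negative in any scenario.

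A further objection is that the covariate brings extra choices (smoothing, missing periods) and mixes treatment histories. The choices can be settled in one written rule. Mixed history makes the covariate a less pure measure of underlying risk, but it does not bias a contrast randomized afterwards.

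**Conclusion.** The point holds as a minor, optional improvement. Item 2 names no covariate, and mortality before month 36 is a valid one already in hand. At CV 0.34 it is worth 0 to about 4 points of power: under 1 point at rho 0.5, and 2.6-3.7 points (2.8-3.9 under the simpler reliability calculation) at rho 1. At the superseded planning CV of 0.51 the range is 0 to 5.9 points (87.0% to 92.9%).

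These figures assume that k in the SAP formula is the between-community CV of true rates, that all six prior intervals are available, and that rho lies between 0 and 1. The documents do not allow rho to be narrowed further.

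**What to change.** In Study B item 2, before months 36-48 are compared by arm, prespecify one covariate: log[(D + a)/(T + a/m)]. D and T are the community's observed deaths and person-years over its available intervals in months 0-36, m is the pooled rate, and a = 1/0.34² = 8.65.

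The rule is defined for communities with no deaths (an expected 0.5-1.8% over 36 months at CV 0.34). It uses only observed person-time and returns log m where there is no history. A missing-period rule is needed because communities may leave and return: "If a community rejoins at a particular phase, it will be included as before".

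Refit the same model for every permutation of the rerandomized labels, so that the test stays valid. Report the unadjusted contrast as a sensitivity analysis, for comparability with Stage 1 and Study A. Original arm may be added to separate prior rate from treatment history, but no precision gain is claimed for it.

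The cost is a short SAP paragraph and one extra parameter against about 620 communities.

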MORDOR 6 Aug-15 to Jan-16	Census Verbal Autopsy Azithro	Census Verbal Autopsy Placebo	Census Azithro NP Swabs, Blood, Stool ^a Malaria Collection ^b	Census Placebo NP Swabs, Blood, Stool ^a Malaria Collection ^b
MORDOR 12 Feb-16 to Jul- 16	Census Verbal Autopsy Azithro	Census Verbal Autopsy Placebo	Census Swabs Blood Stool Anthropometry Azithro	Census Swabs Blood Stool Anthropometry Placebo
MORDOR 18 Aug-16 to Jan-17	Census Verbal Autopsy Azithro	Census Verbal Autopsy Placebo	Census Azithro NP Swabs, Blood, Stool ^a	Census Placebo NP Swabs, Blood, Stool ^a
MORDOR 24 Feb-17 to Jul- 17	Census Verbal Autopsy Azithro^C	Census Verbal Autopsy Azithro^C	Census Swabs Blood Stool Anthropometry Azithro ^C	Census Swabs Blood Stool Anthropometry Azithro ^C

Only children aged 1 month to 60 months per community will be treated

Arms Azithro+ & Control+: swabs, blood testing, and stool samples or rectal swabs from 40 randomly selected children aged 60 months per community; anthropometry from a cohort of children aged 1 to 60 months per community; NP swabs from 40 individuals aged 7 - 12 years (Niger only)

a: Tanzania only

b: Niger only

c: Decision to treat ALL communities with azithromycin at 24-months if there is a significant mortality difference (in preparation for possible contingent study, Niger only)
*: +/- 1 month

Chapter 5: Core and Non-Core Study Elements

An overview of core and non-core elements for the mortality and morbidity study is provided here, but will be described in more detail in the following chapters.

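### Protocol Table 1 and its note c would give azithromycin at month 24 to the 15 Niger Control-Plus communities, which the contingency SAP analyses as still on placebo

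*SAP*

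**What the plan says.** **Protocol 4.3, Table 1.** The Control-Plus column lists placebo at months 0, 6, 12 and 18. In the last row ("MORDOR 24 Feb-17 to Jul- 17") its cell is identical to the Azithro-Plus cell: "Census Swabs Blood Stool Anthropometry Azithro ^C". Note c explains the mark: "Decision to treat ALL communities with azithromycin at 24-months if there is a significant mortality difference". A parenthesis limits this to Niger and ties it to a possible follow-on study. SAP 1.2 puts 15 communities in each Plus arm at each site.

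**Contingency SAP (Niger, years 3-4).** Its section 1 sets the starting condition: "Should the primary analysis of azithromycin to prevent mortality reveal evidence of a benefit". Section 2 (Study A) treats every Niger community at the end of Stage 1 and moves placebo communities to azithromycin at the 24-month visit. It makes no exception for morbidity communities. The Morbidity Study paragraph of section 3 then says: "Analysis of morbidity communities will follow the exact template as Stage I", at a two-sided alpha of 0.05, and "However, the morbidity communities are still receiving placebo". On follow-up it adds: "Note that we will report the full follow-up at 48 months separately from the Stage 1 primary analyses" and "We will also look for secular effects longitudinally over the four years of the full study, as well as phases 5-8 separately". The outcomes it lists are height and weight, weight-for-height z-score, drug resistance and malaria.

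**The concern.** The protocol's dosing rule and the analysis plan describe different treatments for the same 15 communities from month 24. Those communities are the only placebo comparator in the Niger morbidity study. If they were dosed by Table 1, the year 3-4 contrasts would no longer compare azithromycin with communities that had never received it in the trial. This matters most for macrolide resistance, where the comparator's own macrolide exposure bears directly on the contrast. A reader holding only the protocol would take the month-24 Control-Plus treatment to be azithromycin. A reader holding only the contingency SAP would take it to be placebo.

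**Working it through.** The plan gives no figure to reproduce. The check sets the texts side by side and counts treatment rounds.

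**1. Do both texts apply at once?** Note c acts on a significant mortality difference; the contingency study starts on evidence of benefit. The wordings differ, but a significant benefit satisfies both. In that case Table 1 and note c give Control-Plus azithromycin at month 24, while the contingency SAP's morbidity paragraph keeps it on placebo. That paragraph must mean Control-Plus, since Azithro-Plus never received placebo.

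**2. Is Control-Plus exempted anywhere?** No. Note c reaches all Niger communities, the Control-Plus cell carries the mark itself, and section 2 of the contingency SAP has no exception.

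**3. Which text governs?** The morbidity paragraph deals specifically with years 3-4 of the morbidity study. The contingency SAP also cites a 2018 publication of the Stage 1 results (section 3, Study A, item 4b), so its current text postdates the month-24 window of February to July 2017. The protocol change log runs to version 1.9 (27 June 2018) and records no change to the month-24 treatment.

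**4. Exposure under each reading.** This assumes six-monthly rounds continue in years 3-4. Azithro-Plus has rounds at months 0, 6, 12, 18, 24 and 30, which is 6 before month 36. Months 36 and 42 make 8 before month 48.

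| Reading for Control-Plus | Azithromycin rounds before month 36 | Before month 48 |
|---|---|---|
| Morbidity paragraph: placebo throughout | 0 | 0 |
| Table 1 alone: month 24, then placebo | 1 | 1 |
| Contingency SAP sections 2-3 read literally: months 24 and 30 | 2 | 2 to 4 |

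The last row follows section 3 (Study A, item 3), which has the former placebo communities on azithromycin for both intervals from month 24 to month 36. The range of 2 to 4 depends on whether a community re-randomized at month 36 (Study B) goes to placebo (2 + 0) or azithromycin (2 + 2).

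**5. Timing.** Phases 5-8 are the intervals 24-30, 30-36, 36-42 and 42-48. The Table 1 dose would open 1 of these 4. It falls 36 - 24 = 12 months before month 36 and 48 - 24 = 24 months before month 48. These are counts of exposure. The documents give no carry-over figure, so no effect on an estimate can be calculated.

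**6. What is outside the problem.** Protocol 9.1 places swab and stool collection before treatment, and the Table 1 cell lists the dose last, so month-24 outcomes precede it. Protocol Chapter 3 excludes the Plus communities from the mortality comparison.

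**The case against.** The best defence is that the documents largely settle the matter. The contingency paragraph is later and more specific, and its opening word marks an exception. If it is an exception to the all-Niger statement in section 2, it is equally one to note c. The word for continuing placebo implies no interruption, so analysts do have a direct statement. Note c is also conditional, and the month-24 round was past when the contingency SAP reached its current form, so correcting the table cannot change that dose.

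Most of this stands. It shows which text to correct, and it makes continued placebo the likely intent. It does not make the two texts agree: the protocol holds the treatment schedule, and its current version still assigns azithromycin to this arm.

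A reader might infer more than the documents support:

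- **That Control-Plus was in fact given azithromycin.** No passage says so, and the later text points the other way.
- **That the year 3-4 contrasts would become continuous versus delayed-start azithromycin.** That fits the literal reading of contingency SAP sections 2-3. Table 1 alone adds one round, and one round followed by placebo is not a delayed start.
- **That the 36-month rectal-swab analyses (SAP 2.1.3.4 and 2.1.3.5) are compromised.** Those sections do not name their communities, and the contingency SAP elsewhere uses the placebo arm as a label for communities by their Stage 1 assignment.

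**Conclusion.** The inconsistency is real and should be fixed. Given a significant mortality benefit, the protocol's month-24 rule is wrong for the Niger morbidity study. It covers all 15 Control-Plus communities and, if followed, would give them at least one azithromycin round where the analysis plan assumes none. The year 3-4 anthropometry, resistance and malaria contrasts would then lack a never-treated comparator. The round counts rest on six-monthly dosing continuing in years 3-4. How far any estimate would move cannot be stated from the documents. The Stage 1 mortality result and the month-24 morbidity outcomes do not depend on this point.

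**What to change.** 1. **Protocol 4.3, Table 1.** Limit note c to the Niger mortality communities. For the contingent, Niger-only month-24 dose, show placebo in Control-Plus and azithromycin in Azithro-Plus. Keep the Niger-only marker so that no month-24 dose is implied in Malawi or Tanzania.
2. **Contingency SAP, section 2 (Study A).** Insert the word mortality before communities in the all-Niger statement.
3. **Contingency SAP, section 3 (Morbidity Study).** State that Azithro-Plus continues azithromycin and Control-Plus continues placebo through month 48.
4. **Confirm the dose.** Unmasked staff of the data coordinating center should establish from treatment records and the letter key what Control-Plus received at month 24. The assigned-by-given dashboard report (Protocol 18.3) may not be enough. Treatment is handled by letter (Protocol 14.8), so if letters had been reassigned centrally, assigned and given would still agree.
5. **If azithromycin was given.** Describe the 36- and 48-month contrasts by the exposure received (one round then placebo, or delayed start), not as azithromycin versus placebo.

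The cost is one table row and its note, one word, one sentence and a check of existing records. No new data are needed.
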